Each of the volunteers will have to be with 2 or 3 patients at the same time since some authors state that performing support to more than one patient can compensate for a poor relationship with another patient, as well as serve as support in the event of a patient's death (Moulton et al., 2013). The volunteer-patient sessions will be conducted in rooms set up for this purpose in the Carlos Santamaría building of the UPV/EHU. After each session with the patients, each volunteer will have to attend an individual session with the program coordinator [name] to discuss their emotions and reactions after performing the intervention. Psychological supervision of the volunteers is a fundamental part of avoiding retraumatization and the possible appearance of anxious-depressive symptoms (Giese-Davis et al., 2006). Likewise, volunteers will have to participate in group sessions every two months with the rest of the volunteers and the program coordinator [name] in order to strengthen group cohesion, resolve doubts, detect needs and carry out the necessary training.

The patients in this study will be 120 patients with various types of cancer from the Onkologikoa Foundation. Each patient will be matched with a volunteer depending on the type of tumor and medical treatment, since some authors state that for the support program to be effective, the volunteers must have had the same type of tumor and medical treatment as the patients (Pistrang et al., 2012). This is why it will be necessary to homogenize the group of volunteers as much as possible so that the sample of patients has as little variability as possible. The inclusion criteria are: having received the diagnosis of cancer in the last month; not having started medical treatment; the tumor type and medical treatment coinciding with any of the volunteers. The exclusion criteria are: relapse; suffering or having suffered from a serious mental disorder (according to DSM-V criteria). The recruitment of these patients will take place just after the diagnosis, and the professionals of the Onkologikoa Foundation will be in charge of offering this type of intervention to the patients who meet the inclusion criteria of the study.

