Those patients who are interested in participating will be informed about the present research project by the coordinator of the program and by the members of the research team of the Onkologikoa Foundation and it will be these same people who will be in charge of giving the information sheet and the informed consent, and of summoning each participant for the collection of data for the first evaluation. Each participant will be given an evaluation questionnaire of sociodemographic, clinical and psychological variables that he/she will have to bring completed for the day of the appointment. Also, each participant will be given four saliva collection bottles, which they will have to collect four times the day before their appointment. The times of collection of these saliva samples will be upon waking up, 30 minutes later, before lunch (between 13:00 and 13:30) and before dinner (between 20:00 and 20:30). The saliva samples will be collected by the program coordinator at the Onkologikoa Foundation and will be coded and managed by the Biobanko. Subsequently, they will be taken to the Psychobiology laboratory of the UPV/EHU for the determination of different biological variables. In addition,

participants will have to undergo a blood draw on the day of the appointment. The blood collection will be performed by a nurse member of the research team of the Onkologikoa Foundation. The blood samples will be coded and managed by the Biobanko. Subsequently, they will be transferred to the Psychobiology laboratory of the UPV/EHU for the determination of different biological variables.

After this first collection of clinical, psychological and biological data, patients will be randomly selected, through a balanced block randomization method, to be part of the experimental group 1 (EG1) or the experimental group (EG2). As this is a crossover design clinical trial, patients in GE1 will start the peer social support program before the start of medical treatment, while patients in GE2 will start the peer social support program after the end of medical treatment.

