For each GE1 patient, a specific volunteer will be selected based on the patient's tumor type and medical treatment, although depending on the availability of volunteers, other variables will also be taken into account: age, preferred language, time availability, partner, children and socioeconomic level. Once selected, each patient and volunteer will be given a letter of introduction to the other, in order to learn basic information about the patient before the first session. The social peer support program will begin the week prior to the start of medical treatment. There will be a total of eight sessions, one every fifteen days approximately, for a total duration of four months. The duration of each session will be as follows: the first and second sessions will last approximately one hour, the following sessions will last an average of 30 minutes. Patients and volunteers will be given the possibility to request a change of person in case they feel that the bond between them is not adequate.

Once the support program has been completed in EG1, a second evaluation of clinical, psychological and biological variables will be carried out, and, in addition, satisfaction with the intervention program will be evaluated, thanks to the Treatment Satisfaction Questionnaire. In GE2, the evaluation of clinical, psychological and biological variables will be carried out four months after the first evaluation. A third evaluation of all participants will be carried out 15 days after receiving the news of the end of the medical treatment (chemotherapy or radiotherapy). At four months and eight months after the end of medical treatment (chemotherapy or radiotherapy), the fourth and fifth evaluations will be carried out. In each of these evaluations the procedure will be as follows: each participant will be given a questionnaire of psychological measures to fill in before their appointment and four saliva collection tubes, which they will have to collect the day before their appointment. In addition, they will be scheduled for a blood draw and for the collection of the questionnaires and saliva samples.

GE2 patients will participate in the peer support program, but the application of this intervention will take place 15 days after receiving the news of the end of medical treatment. The intervention in this group will have the same characteristics and the same evaluations as those of GE1.

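### A free matching volunteer and time for session 1 before treatment are not confirmed until after randomisation, so by evaluation 2 failure to start as allocated can fall only on EG1

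*Combined protocol and SAP*

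**What the plan says.** All of this is in the METHODS section of the combined protocol and SAP, which writes the groups as both EG1/EG2 and GE1/GE2.

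- **Eligibility.** Diagnosis must be recent, treatment must not have begun, and the third criterion is "the tumor type and medical treatment coinciding with any of the volunteers". A match in principle is therefore required before entry. No criterion mentions a free place or a minimum interval before treatment.
- **Capacity.** "Each of the volunteers will have to be with 2 or 3 patients at the same time". The number of volunteers is not given.
- **Randomisation.** Its place in the sequence is fixed by the phrase "After this first collection of clinical, psychological and biological data". Allocation to EG1 or EG2 is then described as follows: "patients will be randomly selected, through a balanced block randomization method".
- **After randomisation, EG1.** The individual pairing comes next: "For each GE1 patient, a specific volunteer will be selected based on the patient's tumor type and medical treatment, although depending on the availability of". The rest of that sentence says that, as far as supply allows, secondary characteristics such as age and language are weighed too. Introductory letters follow, and then the start rule: "The social peer support program will begin the week prior to the start of medical treatment". The programme has eight sessions over four months.
- **After randomisation, EG2.** The same programme starts 15 days after patients learn that treatment has ended.
- **Evaluation 2.** In EG1 it follows completion of the programme. In EG2 it falls four months on from evaluation 1.

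The documents give no rule for an EG1 patient who cannot start in time. The DATA ANALYSIS section plans an ANOVA between the groups but names no analysis set.

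**The concern.** A patient can meet every entry criterion, complete evaluation 1 and be randomised when every matching volunteer is already full, or when treatment is too close for pairing, letters and session 1 to fit in. If that patient is allocated to EG1, the start rule cannot be carried out. If the same patient is allocated to EG2, nothing is due yet.

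At evaluation 2 the groups differ in whether the programme has been offered, so this is the contrast that speaks to effectiveness. Start failures in one arm only would weaken that contrast. If the patients concerned are removed or replaced, the balance that randomisation provided is lost, because those who cannot start need not resemble those who can. The question of when the programme works best, set out under AIMS, is also touched: EG1 patients who begin after treatment has started have not received the early programme.

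**Working it through.** **Order of events.**

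1. Before randomisation: tumour and treatment match some volunteer; treatment not begun; evaluation 1 done.
2. Randomisation.
3. After randomisation, EG1 only: choose the volunteer, exchange letters, hold session 1 before treatment.
4. Evaluation 2.
5. In the plan's order of evaluations, EG2's programme starts at about evaluation 3.

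Step 3 needs a free place and enough lead time, and neither is secured at step 1. EG2's start comes after step 4, so its own start failures cannot offset EG1's at evaluation 2. This takes the numbered order of evaluations as it stands, that is, treatment is not over before evaluation 2.

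**How long a place is held.** Eight sessions about 15 days apart span 7 × 15 = 105 days from first to last, or 8 × 15 = 120 days counted as eight intervals. A full volunteer may therefore stay full well past a new patient's treatment date.

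**Size, by assumption only.** The plan states a total ("The patients in this study will be 120 patients with various types of cancer from the Onkologikoa Foundation") without inputs, so there is no sample-size calculation to reproduce. Assume 1:1 allocation, so 120 / 2 = 60 per arm, and let *f* be the share of EG1 who do not start as allocated. The documents give no value for *f*; 5% to 20% is an assumed range.

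- Patients affected: 60 × 0.05 = 3 to 60 × 0.20 = 12.
- Analysed as randomised: if non-starters gain a fraction *b* of the full effect, the contrast is multiplied by 1 − *f*(1 − *b*). With *b* = 0 the loss is 5% to 20%. With *b* = 0.5 it is 2.5% to 10%.
- Power (two-sided 5%, normal approximation): 60 per arm has 80% power for (1.96 + 0.84) × √(2/60) = 0.51 SD. Multiplying that effect by 1 − *f* (*b* = 0) gives the power column below.
- Dropped from EG1: if non-starters differ from starters by *g* SD for reasons unrelated to the programme, the EG1 mean shifts by *f* × *g*. With *g* = 0.5 (assumed):

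| *f* | Power if analysed as randomised | Bias if dropped (SD) | Type I error if dropped |
|---|---|---|---|
| 5% | 76% | 0.025 | 5.2% |
| 10% | 71% | 0.05 | 5.8% |
| 20% | 61% | 0.10 | 8.1% |

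**Assessment date.** If EG1 starts *L* days after evaluation 1, its evaluation 2 falls at about day *L* + 105 to *L* + 120, against about day 120 in EG2. An assumed *L* of 30 days gives day 135 to 150. A delayed start therefore moves the assessment in EG1 only, and for an EG1 patient who never starts the text fixes no date at all.

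**The case against.** Much can fairly be said for the plan. A tumour and treatment match is already an entry criterion. Recruitment happens immediately on diagnosis, which favours lead time. The volunteer pool is to be kept as homogeneous as possible, which narrows the case mix to what volunteers can cover. Randomisation itself is unbiased, and nothing in the documents says that non-starters will be dropped.

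Four stronger readings are tempting, and the documents do not support them.

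- **Only EG1 can suffer from a shortage of volunteers.** EG2 needs the same kind of volunteer later, and can also lack one or lose patients during treatment. What is specific to EG1 is the pre-treatment deadline and its consequence at evaluation 2.
- **A patient a few days from treatment cannot follow the EG1 rule.** The text asks for a start in the week before treatment, not for a full week's notice. Session 1 a day or two beforehand satisfies it. Time is tight in such a case, but the rule is not impossible.
- **The tumour match gives way when volunteers are scarce.** The availability clause concerns secondary matching characteristics and does not relax the tumour and treatment match.
- **A known share of EG1 will fail to start.** Volunteer numbers, intervals to treatment and non-start rates are all absent.

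The dilution figure also applies only to the evaluation 2 contrast. Once both groups have had the programme, EG1 non-starts could shrink, widen or reverse the early-versus-late difference.

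All of this limits the point. It leaves the order of steps standing: neither a free place nor sufficient lead time is confirmed before allocation, and only one arm meets the consequence by evaluation 2.

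**Conclusion.** The point holds as a foreseeable, one-sided risk that comes from the order of the procedures. It is not a demonstrated bias. Up to evaluation 2, failure to start as allocated can occur only in EG1. If everyone is analysed as randomised, the cost is a contrast diluted by at most the share who do not start. If non-starters are excluded or replaced, the comparison can be biased, in a direction the documents do not settle. The effect on the timing question has no predictable sign.

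The figures of 3 to 12 patients and a 5% to 20% loss rest on an assumed non-start share, equal arms and, for the loss, no benefit in those affected. The true size could be negligible or larger. The change is still worth making, because it is cheap now and a selective failure to start cannot be undone once patients are randomised.

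**What to change.** Move the check ahead of allocation and apply it to every patient, whichever arm follows. After evaluation 1 and before the allocation is opened, the coordinator confirms that:

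- a volunteer matched on tumour and planned treatment has a free place; and
- the planned treatment date leaves time for session 1 beforehand.

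Randomise only if both hold. State that all randomised patients are analysed in their allocated arm, which also requires a date for evaluation 2 in EG1 patients who do not start or complete the programme. Record the date of session 1 against the start of treatment, so that late starts can be reported.

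The cost is a short amendment and a two-item checklist. Recruitment may be slightly slower. The results will apply only to patients who could have started before treatment, so some fast-treated or harder-to-place patients are left out. The check does not guarantee EG2 patients a place months later, so start delays and unfilled places should be reported for both groups.

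### Evaluation 2 has different triggers in the two arms, and evaluation 4 is not secured as a post-programme measure in EG2

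*Combined protocol and SAP*

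**What the plan says.** All the timing rules are in METHODS of the combined protocol and SAP, which writes the arms as both EG1/EG2 and GE1/GE2.

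- **Programme length:** "There will be a total of eight sessions, one every fifteen days approximately, for a total duration of four months".
- **EG1 start:** "The social peer support program will begin the week prior to the start of medical treatment". Evaluation 1 comes before randomisation. The interval from it to the first session is not fixed.
- **Evaluation 2, EG1:** "Once the support program has been completed in EG1, a second evaluation of clinical, psychological and biological variables will be carried out".
- **Evaluation 2, EG2:** "In GE2, the evaluation of clinical, psychological and biological variables will be carried out four months after the first evaluation".
- **Evaluation 3, both arms:** "A third evaluation of all participants will be carried out 15 days after receiving the news of the end of the medical treatment".
- **EG2 start:** "the application of this intervention will take place 15 days after receiving the news of the end of medical treatment". This is the same time point as evaluation 3, and no order is stated.
- **Evaluations 4 and 5:** "At four months and eight months after the end of medical treatment (chemotherapy or radiotherapy), the fourth and fifth evaluations will be carried out".
- **EG2 in general:** "The intervention in this group will have the same characteristics and the same evaluations as those of GE1".

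No visit windows are given. AIMS asks for the immediate and long-term effects and for the point in the illness at which the programme works best. DATA ANALYSIS controls for type and duration of medical treatment and for pharmacological treatment, but not for visit timing.

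**The concern.** Evaluation 2 is the first comparison of patients who have had the programme with patients who have not. If its date follows session delivery in one arm and the calendar in the other, time since diagnosis and phase of treatment can differ by arm at that visit. Controlling for treatment type and duration does not realign the dates.

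The question of best timing needs a measure soon after the programme in each arm. EG1 has one. In EG2 the only dated visit near the end of the programme is evaluation 4. It runs on a different clock (end of treatment) from the programme (news of the end of treatment). If it falls before the last session, the comparison sets a finished programme against an unfinished one.

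**Working it through.** **Inputs from METHODS:** eight sessions; spacing s of about 15 days; stated length four months; EG2 start 15 days after the news; evaluation 4 four months after treatment end. I take four months, M, as 120 days (30-day months) to 121.75 days (4 × 365.25/12).

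**Assumed, because the documents do not give them:** gap g from evaluation 1 to session 1 of 0 to 30 days; news lag L of 0, 7 or 14 days; s of 14 or 16 days as mild departures from 15.

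**The plan's own figure.** 8 × 15 = 120 days = 3.94 months, which reproduces the stated four months. First to last session is 7 × 15 = 105 days = 3.45 months. The stated period therefore includes a final 15 days with no session.

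**Evaluation 2: EG1 date minus EG2 date.**
- On the nominal four-month period: g + M - M = g, so 0 to +30 days.
- If EG1 is measured straight after session 8: g + 7s - M.

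| s | M = 121.75 | M = 120 |
|---|---|---|
| 14 | -23.75 to +6.25 | -22 to +8 |
| 15 | -16.75 to +13.25 | -15 to +15 |
| 16 | -9.75 to +20.25 | -8 to +22 |

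On the second formula, at 15-day spacing, the arms coincide only if g = M - 105 = 15 to 16.75 days.

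**Evaluation 4: margin after EG2's session 8.** Session 8 falls on day 15 + 7s + L after treatment end, so the margin is M - 15 - 7s - L. At s = 15 and L = 0, session 8 is on day 15 + 105 = 120.

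| s | L = 0 | L = 7 | L = 14 |
|---|---|---|---|
| 14 | 7 to 8.75 | 0 to 1.75 | -7 to -5.25 |
| 15 | 0 to 1.75 | -7 to -5.25 | -14 to -12.25 |
| 16 | -7 to -5.25 | -14 to -12.25 | -21 to -19.25 |

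With no lag, the margin is non-negative only if mean spacing is at most (M - 15)/7 = 15.0 to 15.25 days. On the stated four-month period the programme ends on day 15 + M, which is 15 days after evaluation 4.

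Sessions held by evaluation 4 are min(8, floor((M - 15 - L)/s) + 1). For L = 0, 7, 14 this gives 8, 8, 7 at s = 14; 8, 7, 7 at s = 15; and 7, 7, 6 at s = 16.

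**Short treatment (conditional, as no durations are given).** Count days from treatment start, with session 1 on day -7. Evaluation 1 is then on day -7 - g, EG2's evaluation 2 on day M - 7 - g, and EG2's start on day T + 15 + L, where T is treatment duration. EG2 starts before its own evaluation 2 if T < M - 22 - g - L. With L = 0 that is 98 to 99.75 days at g = 0 and 68 to 69.75 at g = 30: about 70 to 100 days, less any news lag.

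**The case against.** The case for the plan is substantial.

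- **Alignment is plainly intended.** Both evaluation 2 rules point to about four months, and the offsets straddle zero with no shown direction or effect on any outcome. This stands. The fault is that timing is uncontrolled and can differ by arm; no large gap is planned.
- **Completers only.** A reader might infer that EG1's evaluation 2 is restricted to patients who attend all eight sessions. The text does not establish that. It can equally mean the end of the group's four-month programme period, and attendance is not made a condition of measurement. What remains is that no rule covers patients who stop early.
- **The 15-day overrun.** A reader might infer that evaluation 4 always interrupts EG2's programme. At exact 15-day spacing with no lag it does not, because the extra 15 days contain no session and all eight have been held. The negative margins need wider spacing or a news lag, and the lags are assumed.
- **EG2 may have its own completion visit.** The statement that it has the same evaluations as the other arm can be read that way. But it gives no date, and an extra visit would have to be squared with the shared evaluation 4.
- **Evaluation 5 is post-programme in EG2.** True, but at 15-day spacing with no lag it comes 2M - 120 = 120 to 123.5 days after session 8. It serves the long-term aim, not the immediate one.
- **Short treatment is speculative.** It is conditional on unstated durations, and a news lag that worsens the evaluation 4 margin eases this problem. It is a secondary remark.

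**Conclusion.** The point holds as a scheduling fault that should be corrected. It does not invalidate the design.

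From the documents alone: evaluation 2 has different triggers by arm, evaluation 4 and EG2's programme run on different clocks, and the best-case margin is 0 to 2 days although spacing is only approximate. One extra day between sessions turns that margin into -7 to -5 days. The one sentence that might give EG2 a completion visit carries no date.

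The size of the evaluation 2 offset (about -17 to +15 days at 15-day spacing) rests on the assumed 0 to 30 day gap. The larger negative margins at evaluation 4 rest on assumed lags and spacing. The documents do not show that EG1 is measured in completers only, that evaluation 4 necessarily precedes EG2's last session, or that short treatment will occur.

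**What to change.** Move visits only; the programme is untouched and the number of dated visits stays the same.

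1. **Evaluation 2:** do it in every randomised patient of both arms, whatever the sessions attended, on one anchor. An example is four months after the actual start of medical treatment, or four months after evaluation 1 if treatment does not start. With session 1 on day -7 to -1, EG1's session 8 falls on day 98 to 104 at 15-day spacing. That is 16 to 24 days before a visit on day 120 to 121.75 (9 to 17 days before it at 16-day spacing).
2. **Evaluations 3 to 5:** do evaluation 3 before EG2's first session, evaluation 4 four months after evaluation 3, and evaluation 5 four months after evaluation 4, in both arms. The margin after EG2's session 8 becomes M - 7s: 15 to 17 days at 15-day spacing and 8 to 10 at 16-day. The news lag cancels. On the nominal four-month period the margin is zero instead of -15 days.
3. **Reconcile** the statement that EG2 has the same evaluations with these dates.

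**Cost:** a short amendment to the visit schedule. Evaluations 4 and 5 move 15 days later plus any news lag (22 or 29 days for an assumed lag of 7 or 14). Time from evaluation 1 to evaluation 2 varies between patients, but by the same rule in both arms. Heavy session slippage can still overlap a visit.

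With short treatment EG2 can still start before evaluation 2. Under the example anchor this happens if T < M - 15 - L, that is below 105 to 106.75 days less any lag, somewhat more often than now. Evaluation 3 would then also fall before evaluation 2. The number of such patients should be reported by arm.

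### When treatment is short, GE2 starts the support programme before its own evaluation 2, because the two run on separate clocks that no rule ties together

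*Combined protocol and SAP*

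**What the plan says.** All the timing rules are in the METHODS section. (The protocol writes the groups as both EG and GE; EG1 and GE2 are used here.)

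- Evaluation 1 comes before allocation: "After this first collection of clinical, psychological and biological data, patients will be randomly selected, through a balanced block randomization method".
- EG1's programme: "The social peer support program will begin the week prior to the start of medical treatment". Its length: "There will be a total of eight sessions, one every fifteen days approximately, for a total duration of four months".
- Evaluation 2 in EG1 follows completion: "Once the support program has been completed in EG1, a second evaluation of clinical, psychological and biological variables will be carried out". In GE2 it is a calendar visit: "In GE2, the evaluation of clinical, psychological and biological variables will be carried out four months after the first evaluation".
- Evaluation 3: "A third evaluation of all participants will be carried out 15 days after receiving the news of the end of the medical treatment".
- GE2's programme: "the application of this intervention will take place 15 days after receiving the news of the end of medical treatment".

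On entry, the patient-level timing conditions are "having received the diagnosis of cancer in the last month; not having started medical treatment". The other conditions are a volunteer with matching tumour and treatment, no relapse and no serious mental disorder. None concerns how long treatment will last. The DATA ANALYSIS section adjusts every analysis for kind and length of treatment, studies the programme effect by repeated measures within patients, and compares the groups by ANOVA without naming an evaluation.

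**The concern.** The AIMS section asks for the immediate effect of the programme. The natural randomised evidence on that is evaluation 2, where EG1 has just finished and GE2 should not have begun. This works only if GE2's start, which depends on treatment ending, falls after a date fixed by the calendar. The sample covers various cancers, and the end of treatment is defined by chemotherapy or radiotherapy, so a patient with a single short course can enter. For that patient the rules as written give evaluation 1, then evaluation 3 and the start of GE2's support, then evaluation 2.

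Two things are at stake. The between-group difference at evaluation 2 would set supported patients against partly supported ones. The numbered evaluations would also no longer be in time order for some patients in a repeated-measures analysis.

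**Working it through.** The plan states no figure to reproduce, so the check is calendar arithmetic from its own anchors.

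**Inputs.** From METHODS: GE2's evaluation 2 at four months (120 days at 30 days a month; 121.8 at calendar length); evaluation 3 and GE2's start at the news plus 15 days; eight sessions 15 days apart. Assumed, because not given: *g*, days from evaluation 1 to treatment start (7 to 30); *L*, days from end of treatment to the news (0 to 14); EG1's first session seven days before treatment. *D* is treatment duration in days.

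**GE2.** Programme start = evaluation 3 = g + D + L + 15. This precedes day 120 when D < 105 − g − L.

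| g | cut-off, L = 0 | cut-off, L = 14 |
|---|---|---|
| 7 | 98 | 84 |
| 14 | 91 | 77 |
| 21 | 84 | 70 |
| 30 | 75 | 61 |

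Calendar months add 1.8 days, so the range is 62.8 to 99.8 days (2.06 to 3.28 months).

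**EG1.** Evaluation 2 falls at g − 7 + P, where P is programme length. Evaluation 3 falls at g + D + L + 15. Evaluation 3 comes before completion when D < P − 22 − L, whatever g is. With L = 0:

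- P = 7 intervals × 15 = 105 days gives D < 83.
- P = the stated four months (121.8 days) gives D < 99.8.

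**Both at once.** With 15-day spacing, the lowest cut-offs in the assumed range are 61 days for GE2 (105 − 30 − 14) and 69 days for EG1 (83 − 14). Below about 61 days, both failures occur for every combination considered.

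**Sessions received**, for g = 14 and L = 0:

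| D (days) | GE2 start and evaluation 3 (day) | GE2 sessions before day 120 | EG1 sessions before evaluation 3 |
|---|---|---|---|
| 21 | 50 | 5 of 8 | 3 of 8 |
| 42 | 71 | 4 of 8 | 5 of 8 |
| 63 | 92 | 2 of 8 | 6 of 8 |
| 84 | 113 | 1 of 8 | 8 of 8 |
| 105 | 134 | 0 | 8 of 8 |

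For D = 42, for example, GE2's sessions fall on days 71, 86, 101 and 116. EG1's fall on days 7, 22, 37, 52 and 67.

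**Dilution, hypothetical only.** If benefit were proportional to sessions, and a share f of patients had k GE2 sessions before evaluation 2, the retained difference would be 1 − f × k/8. With f = 0.2 and k = 1 this is 0.975; with f = 0.6 and k = 4 it is 0.70. Neither f nor the distribution of k can be taken from the documents.

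**The case against.** Several objections have force.

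- **The cut-off is not one number.** A reader might infer that every patient treated for under three months is affected. The documents do not support that. The cut-off depends on a gap and a news delay that are not stated; with a 30-day gap and no delay it is 75 days. The 7-day gap is itself an extreme, since it puts EG1's first session on the day of evaluation 1, and randomisation, choice of volunteer and letters of introduction must come first.
- **Evaluation 3 sometimes still works.** At D = 84 and g = 14, EG1 has finished on day 112 and GE2 begins on day 113, so evaluation 3 compares a completed programme with none. This stands, but the band is narrow.
- **The role of evaluation 2 is inferred.** No section designates it as the supported-versus-unsupported comparison. The ANOVA names no time point, and the programme effect is assigned to within-patient analysis. Nor do the documents say how evaluations will be coded, so mis-ordered data are a risk and not a stated procedure.
- **The plan has relevant provisions.** METHODS aims for a homogeneous sample and counts surgery as treatment, which may lengthen some courses. DATA ANALYSIS adjusts for treatment length. Homogeneity of tumour and treatment type does not guarantee duration, however. Adjustment for duration shifts outcome levels; it does not turn partly supported GE2 patients into unsupported ones.

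None of this ties the two clocks together. The objections limit the scope and size of the point without removing it.

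**Conclusion.** The point holds for short courses. The rules in METHODS, followed as written, have GE2 starting support before its evaluation 2, with evaluation 3 due before evaluation 2, whenever treatment lasts less than about 105 − g − L days (roughly 2 to 3.3 months under the assumed ranges). In EG1, evaluation 3 precedes completion below about 83 days (15-day spacing) to 100 days (the stated four months), less any news delay. Where both apply, no evaluation compares a completed programme with none.

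If the programme works, the effect is to dilute the group difference at evaluation 2. A reader might take the retained fractions above as an estimate of the loss. They are not one: the documents give no treatment durations and no share of short courses, so the size cannot be computed. The ordering gap is certain from the text; its practical weight depends on case mix.

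**What to change.** 1. In METHODS, reconcile the rules for evaluation 2, evaluation 3 and GE2's programme start, stating which clock governs the evaluations when treatment ends early. This concerns the order of measurements and asks for no change to when support is given.
2. Record each patient's planned end of treatment before randomisation. Planned treatment type is already needed for matching to a volunteer.
3. In DATA ANALYSIS, prespecify the EG1 versus GE2 comparison by that class. Where planned treatment ends at least 3.5 months after evaluation 1, use evaluation 2 (105 + 15 = day 120, so *g* drops out and a news delay only adds margin). Otherwise use the existing evaluation 3, completed in GE2 before its first session, and report it as partial exposure where EG1 has not finished.
4. Keep patients in their planned class whatever their actual treatment length, so that the comparison stays randomised.
5. Use actual evaluation dates in the repeated-measures analysis.

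The cost is protocol and analysis wording plus one baseline item, with no added visit. The downsides are that the full-programme comparison rests on fewer of the 120 patients, the short-course comparison partly reflects an unfinished programme, and some patients will depart from their planned duration.
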